1 ABSTRACT (250 WORDS)

Background: Dietary guidelines are intended to inform and aid the general public, with the aim of improving healthy diets and reducing health risk. The effectiveness of these guidelines however is rarely investigated.

Aim: This work investigates the effects of three different types of dietary recommendations for reducing free sugars, on free sugar intakes over 12 weeks. Secondary aims will also investigate how these different recommendations affect secondary outcomes, outcomes in subsets of the trial population, and identify barriers and facilitators to dietary change.

Methods: Using a randomised controlled parallel-group trial with three intervention and one control arm, 240 individuals consuming >5% total energy intake from free sugars will be randomized to receive: nutrient-based, nutrient- and food-based, nutrient-, food- and food-substitution-based recommendations or no recommendations, with outcomes assessed for the following 12 weeks. Our primary outcomes are free sugar intakes and adherence to the recommendations. Secondary outcomes are daily energy intake, dietary composition, anthropometry, sweet food perceptions and preferences, sweet food choice, attitudes towards sweet foods, eating behaviour, and food choice, knowledge and lifestyle variables, quality of life, adverse events, and barriers and facilitators towards intervention adherence.

Results: Data will contribute to three distinct analyses: 1) Analyses to investigate the effects of the three different dietary recommendations versus control; 2) Analyses of the effects of the dietary recommendations in different population subgroups, and 3) Investigation of the barriers and facilitators to success.

Conclusion: This work offers new perspectives on the efficacy of different dietary recommendations to enact behaviour change.

2 INTRODUCTION

Extensive epidemiological evidence supports a relationship between dietary intakes and the incidence, prevalence and severity of non-communicable diseases (Afshin et al., 2019). Thus, the prevention and treatment of non-communicable diseases may be aided through greater population-based adherence to healthy diets (Brunner et al., 2007; Eriksen et al., 2018).

One strategy for improving diets on a population-wide basis lies in the provision of dietary guidelines. With the evidence for benefit primarily based on nutrients, early dietary recommendations focused on nutrient intakes, e.g. salt, fat, folate. These guidelines adapted nutrient daily reference intake values into simple messages for the public (Public Health England, 2016). The UK's salt reduction programme, for example, relied on simple nutrient-based recommendations such as to 'check food labels' (He et al., 2014). In combination with industry reformulation, and a straightforward monitoring programme, successful reductions in salt intakes and population blood pressure were observed (He et al., 2014), but progress has stalled since 2011 (He et al., 2019; National Diet and Nutrition Survey, 2020).

In 1998, the World Health Organization (WHO) and Food and Agriculture Organization (FAO) recommended that consumer guidelines should be based on foods. The rationale being that foods, not nutrients, make up dietary choices and that encouraging change to whole dietary patterns would benefit multiple single nutrient goals (World Health

Organisation et al., 1998). National food-based dietary guidelines (FBDG) now exist in over 90 countries (Herforth et al., 2019).

The majority of FBDG are produced from scientific data, versions of previous guidance, and guidelines in other countries (Blake et al., 2018). For example, Public Health England (PHE) recently reformulated the UK's 'Eatwell guide' in response to a national free sugar reduction programme (Public Health England, 2014) and revised dietary recommendations (Scientific Advisory Committee on Nutrition, 2015). Linear programming of intake and food composition data were used to identify foods and food groups, and models were created to identify the fewest number of dietary changes required to meet national daily reference intake values (Public Health England, 2016). The new guidance was then evaluated for understanding in consumer research interviews (Public Health England, 2016), but no real-world field testing was undertaken. This lack of testing may contribute to low uptake and adherence to FBDG (Leme et al., 2021; Yau et al., 2019), suggesting a need for greater rigour in assessing the efficacy and effectiveness of FBDG (Brown et al., 2011).

Limited evidence also suggests that the use of food substitutions may aid FBDG. Pilot evidence suggests that campaigns around snack substitutions may enact dietary change (Juszczyk & Gillison, 2018), and online supermarket-based studies report benefits to the contents of shopping baskets by altering the order of the offered food and suggesting lower saturated fat options (Koutoukidis et al., 2019). However, other studies have found little benefit from food substitution strategies (Forwood et al., 2015).

The proposed study will investigate the effectiveness of nutrient-, food-, and food-substitution-based recommendations for reducing free sugar intakes. Increased consumption of dietary sugars and associations with increased risk of dental carries, non-communicable diseases and excess weight (Ahmad et al., 2020; Monnard and Grasser, 2018; Scientific Advisory Committee on Nutrition, 2015; World Health Organisation, 2015) have resulted in the recommendation that intakes of '*free sugars should not exceed 5% of total dietary energy*' (Scientific Advisory Committee on Nutrition, 2015: page 196). Effects of the differing recommendations will be assessed on free sugar intakes, dietary profiles and sweet taste outcomes in adults consuming >5% total energy intake (TEI) from free sugars.

3 METHODS AND DESIGN

This trial is a randomised controlled parallel-group trial with three intervention arms and one control arm. The primary purpose is to assess the effects of three different types of dietary recommendations for reducing free sugars, on free sugar intakes over 12 weeks, in individuals consuming >5% TEI from free sugars. Secondary aims will investigate how these different recommendations affect secondary outcomes, outcomes in subsets of the trial population, and will identify potential barriers and facilitators to dietary change.

3.1 ETHICAL CONSIDERATIONS

The trial received ethical approval from the Research Ethics Committee of Bournemouth University, UK (ref: 30612) on 28.04.20 (with amendments approved on 29.03.21), and registered on Clinicaltrials.gov (ID: NCT04816955) on 24.03.21. The trial will be run in accordance with the Declaration of Helsinki (1983), the Ethical Guidelines of the British Psychological Society, and Bournemouth University's Research Ethics Code of Practice. All participants will provide written informed consent prior to participation.

4 PARTICIPANTS

4.1 RECRUITMENT AND ELIGIBILITY

We aim to recruit 240 male and female participants from the general community residing in the South of England. Individuals will be eligible for trial inclusion if they are: aged 18-65 years, consuming >5%TEI from free sugars, able to provide informed consent and complete all trial measures. Exclusion criteria are pregnancy or breastfeeding; underweight (BMI<18.5kg/m²); pre-existing medical conditions affecting swallowing ability, taste and/or smell perception; currently, or within the previous three months of starting the trial, following a specific dietary programme (e.g. slimming world); currently, or within the previous three months, smoking; pre-existing clinical conditions, including allergies, diabetes mellitus, eating disorders, Crohn's disease, leading to the use of external nutritional advice and dietary restrictions.

4.2 SAMPLE SIZE

Sample size equations are powered at 80% for an alpha of 0.05 to test for a 2% change in percentage free sugar intakes from baseline to trial end (Whitley and Ball, 2002). Due to a lack of literature on the use of dietary recommendations for reducing free sugar intakes at trial conception, sample size equations were based on the reported effects of a trial on the use of dietary recommendations for reducing saturated fat content (Smith et al., 2015). The highest standard deviation reported in these data was used to calculate a standardised difference (0.8) and then gain sample size estimates (Whitley and Ball, 2002). Two hundred forty participants will be enrolled into the study, with 60 participants allocated to each trial arm, with an attrition allowance of 20%.

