8.1 ANALYSES ONE: EFFECTS OF THE DIFFERENT DIETARY RECOMMENDATIONS

To test the effects of the different dietary recommendations, a series of multiple regression analyses will be run. A separate analysis will be run for each outcome variable, where the outcome at week 12 will be predicted by trial arm (intervention/control) and outcome variable at baseline. Additional independent variables will also be included in each analysis as possible, to include: demographic variables, total energy intakes, sweet liker status; PROP taster status; and attitudes to sweet foods, eating behaviour and food choice.

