Current literature suggests the optimal number of imputations varies between 5-20, with limited benefit over 5. Additional literature supports the number of imputations matching the percentage of attrition. Therefore, the number of imputations for the main analyses was set at 20 representing both the upper recommendation and percentage attrition.

Updates to SPSS now allow random selection of the closest of over >1 donor. Existing methodology and the amount of imputations suggest imputations via Predictive Mean Modelling are selected from the 5 closest donors making this more statistically robust than previous methods.

Before completing multiple imputation, the pattern of missing data was checked. Endpoint data presented as missing in a monotonic pattern. When imputing missing data values in SPSS the custom 'fully conditional specification (FCS)' in methods was selected over monotone. This was because FCS is suitable for both monotone and non-monotone patterned data and introduces Bayesian stochastic regression imputation as part of the predictive means multiple imputation methods. The benefit of this method results in imputed data being taken from both a donor and then adjusted to introduce a level of variability rather than just a copied result. Maximum iterations were set as 50 with FCS convergence checked post imputation. For all applicable statistical tests, analyses were run on each imputed dataset, with values pooled post analysis. This is because a pooled dataset prior to analysis does not just represent the average but retains the variability of the individual imputed datasets.

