BLNFS, BLDGendermale1female2, BLBMI, BLNEnergykcal, BLNCarbohydrateg, BLNProteing, BLNFatg, BLN Sugarsg, BLNFreeSugarsg, BLNFibreg, BLNSaturatedFatg, BLSSodiumNamg, BLWeightkg, BLWaistcircumferencecm, BLLTEShealthscore, BLFCQ1Health, BLFCQ2Mood, BLFCQ3Convenience, BLFCQ4SensoryAppeal, BLFCQ5NaturalContent, BLFC1Q6Price, BLFCQ7WeightControl, BLFCQ8Familiarity, BLFCQ19EthicalConcern, BLSQPC1Personalimpact, BLSQPC2Personalmanagement, BLSQPC3Nonchalance, BLSQPC4Negativity, BLSQPC5Perceivedunderstanding, BLSQPC6PerceivedNonautonomy, BLSF36PCS, BLSF36MCS, BLTSEQ CR, BLTSEQQUE, BLTSEQEE. *Followed by imputation only variables

Get pooled descriptives for analysis / comparison to my values.

1. Data - Split file
 - a. Click split file in ComA1_imp
 - b. Click compare groups
 - c. By imputation number_variable
 - d. Ok
2. Analyze – Descriptive statistics
 - a. Descriptives
 - b. Input all BL and EP variables apart from BL OG FS%.
 - c. Scroll to bottom of output table for pooled means – SD will be calculated from average of 20 imputations at a later date and are not shown here.

BLINDING

The main researcher had no knowledge of allocated groups of participants and was blinded during all data handling and imputation.

DATA ANALYSIS

Outcomes

Primary outcomes were % TEI from free sugars (%FS), and adherence to the recommendations at 12 weeks. Secondary outcomes were dietary profiles (daily energy intake, dietary composition, food consumption), anthropometry, sweet food perceptions and preferences, sweet food choice, attitudes to sweet foods, attitudes towards eating behaviour, motives for food choice, knowledge and lifestyle variables, quality of life and adverse events at week 12; change between baseline and week 12 in key outcomes (%FS, daily energy intake, sugar-sweetened and sweetener-sweetened food consumption, anthropometry), %FS, adherence, dietary profiles and barriers and facilitators towards intervention adherence and success/failure in achieving the recommendations (subset only) at weeks 1, 2, 4 and 8. Demographic variables, and sweet taste sensitivity, sweet liker status and PROP (bitter taste) status were also assessed at baseline, to aid in the interpretation of all outcomes, considering associations between these variables and sweet taste perceptions, liking and food intakes (Jayasinghe et al., 2017; Yeomans et al., 2009).

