Three distinct analyses were pre-specified in advance: 1) Analyses of the population as a whole to investigate the effects of the three different types of dietary recommendation versus control; 2) Analyses of the effects of the dietary recommendations in different population subgroups, and 3) Investigation of the barriers and facilitators to success.

Data presentation

Data will be presented as mean \pm standard deviation in all cases, unless stated. Values will be considered significant at the $p<0.05$ level. Before completing analyses, data will be checked for normality. The data set is large, $N=242$, thus a normal distribution will be assumed. Where assumptions of homogeneity of variance are violated (Levene's test $p<0.05$), statistics will be taken from analyses conducted assuming non-equal variances. Bonferroni corrections for multiple testing will be applied to data where tests were not pre-specified in the study protocol. Where multiple regression analyses are used, all variables will be checked for multicollinearity using correlation cut-offs of <0.7 . Pearson correlation values will be used for all continuous variables, and Spearman correlations for categorical variables.

Participant characteristics

Details of study completion will be provided and a CONSORT diagram created detailing number randomized to each group, number completing the study in each group, drop out and number included in all analyses.

Characteristics will be given for the whole sample and for each trial group.

Analyses One: Quantitative Data

For analyses one, multiple regression analyses will be used. Analyses will be conducted for both primary outcomes, for key secondary outcomes - daily energy intake, sugar-sweetened food intake, LCS-sweetened food intake, body weight, waist circumference, and adverse events; and change (baseline - week 12) data for these outcomes; and for other secondary outcomes (dietary

composition, sweet food perceptions and preferences, sweet food choice, attitudes to sweet foods, attitudes towards eating behaviour, motives for food choice, knowledge and lifestyle variables, quality of life) if differences are found in the sample as a whole from baseline to week 12. This will reduce the number of exploratory tests undertaken. Differences from baseline to week 12 will be investigated by paired t-tests. Primary outcomes and outcomes associated with dietary composition will also be investigated in the same manner at weeks 1, 2, 4 and 8.

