Primary models will include gender, age, control/intervention group, baseline %FS, baseline body weight (as randomization variables), and baseline variable of interest. In analyses for %FS, sugar-sweetened food intake, LCS-sweetened food intake, body weight and waist circumference, TEI at Week 12 and physical activity at Week 12 will also be included. Secondary models will also include any additional variable that correlates with each outcome when assessed independently. All variables measured will be considered as secondary variables. Effects for all continuous variables will be investigated using linear multiple regression. Effects for adherence will be investigated using logistic regression to predict adherent vs not adherent.

Analyses Two: Quantitative Data

For analyses two, analyses one will be repeated for demographic groups where significant associations for these variables were found in analyses one. Analyses will only be conducted if significant associations are reported. If no significant associations with demographic variables are found, these analyses will not be completed. These analyses are intended to demonstrate differing effects of the intervention/s in different population groups.

Analyses Three: Qualitative Data

Analyses three will investigate the qualitative data collected from a subset of participants using solo interviews. These interviews were scheduled for completion in a sample of 80 participants from different intervention groups and at different time points. These analyses will be undertaken using a thematic framework analysis. First, a random sample of interviews will be analysed inductively using thematic analysis to identify codes. These codes will be used to create a framework and the framework then applied to all interviews.

Framework analysis has been chosen as a suitable analytical method for evaluating the qualitative interview data gathered, due to an interest in individual experiences and seeks to identify the different factors (barriers or facilitators) that contributed to successful or unsuccessful dietary change (Braun & Clark, 2013). The practical methods for conducting framework analysis follow a methodology as outlined below.

Framework analysis (Braun & Clarke, 2006; 2013; Gale et al, 2013).

Phase 1 'Familiarizing yourself: Transcribing data (if necessary), reading and re-reading the data, noting down with your data: initial ideas'.

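### The inputs in Protocol 4.2 give about 32-33 enrolled per arm, not 60, so the stated 80% power does not belong to the stated size; secondarily, the SAP leaves the primary tests uncorrected and the group term undefined

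*Protocol*

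**What the plan says.** **Sample size (Protocol 4.2).** The calculation is described as follows: "Sample size equations are powered at 80% for an alpha of 0.05 to test for a 2% change in percentage free sugar intakes". The spread is borrowed from a dietary trial on saturated fat: "The highest standard deviation reported in these data was used to calculate a standardised difference (0.8) and then gain sample size estimates". The result is: "Two hundred forty participants will be enrolled into the study, with 60 participants allocated to each trial arm, with an attrition allowance of 20" per cent. The section does not give the SD, the sidedness, the number needed before attrition, which contrast between arms is powered, or any basis for adherence, the other primary outcome.

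**Primary tests.** The SAP's Outcomes section says: "Primary outcomes were % TEI from free sugars (%FS), and adherence to the recommendations at 12 weeks". Its Data presentation section sets significance at p<0.05 and confines Bonferroni correction to tests that the protocol did not pre-specify. No other multiplicity rule appears.

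**Group term.** Protocol 8.1 has "outcome at week 12 will be predicted by trial arm (intervention/control) and outcome variable at baseline". The SAP, under Analyses One, has "Primary models will include gender, age, control/intervention group, baseline %FS, baseline body weight (as randomization variables), and baseline variable of interest". Both can be read as a single pooled indicator. The SAP's Data analysis section, however, describes "Analyses of the population as a whole to investigate the effects of the three different types of dietary recommendation versus control", which reads as three contrasts.

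**The concern.** A sample-size paragraph should let a reader go from the inputs to the number. Here the inputs lead to roughly half the stated number. A reader therefore cannot tell whether 80% power or 60 per arm describes the trial, or what difference the trial was built to detect. This matters most for a null result: excluding a difference of 0.8 SD is a much weaker statement than excluding one of 0.58 SD.

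The SAP point is separate and bears on inference. The primary tests are pre-specified, so they fall outside the Bonferroni rule. Because the coding of the group term is open, the number of primary tests could be settled after results are seen.

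**Working it through.** **Inputs.** From Protocol 4.2: power 80%, alpha 0.05, effect 2% TEI, standardised difference d = 0.8, attrition 20%, 60 per arm. Implied SD = 2/0.8 = 2.5% TEI. Assumed: two-sided test, two arms compared.

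**1. Attempt to reproduce 60.** Normal approximation: n = 2(z₀.₉₇₅ + z₀.₈₀)²/d² = 2(1.960 + 0.842)²/0.64 = 24.5, so 25 evaluable per arm. The t-test gives 25.5, so 26.
- Dividing by 0.8: 25/0.8 = 31.25 and 26/0.8 = 32.5, so 32 or 33 enrolled (128 to 132 over four arms).
- Multiplying by 1.2 instead: 30 to 32 enrolled.

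The stated 60 is not reproduced.

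**2. Other readings of the same inputs (80% power, d = 0.8 unless shown).**

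| Reading | Enrolled per arm |
|---|---|
| One-sided | 25-27 |
| Paired | 18-19 |
| d rounded from 0.75 to 0.85 | 29-37 |
| Four-arm omnibus F, range over patterns of means (f = 0.40 to 0.283) | about 23-45 |
| Bonferroni, three tests (t-test) | 43-44 |
| Bonferroni, six tests (t-test) | 50 |

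None reaches 60.

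**3. Routes that do arrive near 60.** A two-arm total used as a per-arm figure gives it exactly: 2 × 25 = 50, and 50 × 1.2 = 60. Bonferroni for 12 tests gives 58. Higher power with a split alpha also comes close (90% power with six tests, 59-63; 95% power with two tests, 58-62). The documents state none of these.

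**4. What 60 per arm delivers.** The evaluable number is 60 × 0.8 = 48, or 60/1.2 = 50 if the allowance was added as n × 1.2.
- Power at d = 0.8 with 48: 0.8 × √(48/2) = 3.92, and Φ(3.92 − 1.96) = 0.975; t-test 0.972. With 50, the t-test gives 0.977.
- Difference detectable with 80% power (t-test): d = 0.578 with 48 and 0.566 with 50. At SD 2.5 these are 1.44% and 1.41% TEI.
- For 48 to be the 80% power size for 2% TEI, the SD would have to be 2/0.578 = 3.46, not 2.5.
- Power for 2% TEI with 48 per arm at SD 2.5, 3, 3.5 and 4: 97%, 90%, 79% and 68%. The SDs above 2.5 are assumptions, not document figures.

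All of these are for unadjusted t-tests. The planned analysis is a baseline-adjusted regression with multiple imputation.

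**5. Chance of at least one false primary claim.** All nulls true, each test at 0.05, a claim allowed on either outcome, shared control group, correlation r between outcomes assumed (1,000,000 simulations).

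| Group term | r = 0 | r = 0.5 | r = 0.9 |
|---|---|---|---|
| One pooled term, two outcomes | 0.097 | 0.091 | 0.071 |
| Three contrasts, two outcomes | 0.236 | 0.219 | 0.173 |

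The pooled figure at r = 0 agrees with 1 − 0.95² = 0.0975. Three contrasts on free sugar intake alone give about 0.125. Protocol 6.1 and 6.2 derive both outcomes from diet diaries, so the high-correlation end is the more plausible.

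**The case against.** **An unstated margin is possible.** Section 4.2 does not call 60 the minimum, and Protocol 8.2 plans subgroup analyses where numbers allow. This stands as a possibility, but the section gives no such reason.

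**A reader might infer that an input was misreported.** The documents do not support this. If a two-arm total was used per arm, every stated input could be correct, and altering one would introduce an error.

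**A reader might infer that the trial is too small.** The opposite holds on the plan's own inputs: free sugar intake has more power than stated.

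**The 48 is a convention.** It is one reading of the attrition allowance; 50 is the other. The SAP's imputation section says "Therefore, the number of imputations for the main analyses was set at 20 representing both the upper recommendation and percentage attrition", which fits attrition of about 20% but does not give evaluable numbers by arm. The conclusion is the same under either.

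**It is late.** The SAP already gives N=242, so a power statement made now is retrospective and changes no recruitment decision. That limits the weight of the point, but the statement in 4.2 is still wrong as written.

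**On multiplicity.** The inflation presumes that either outcome alone can carry a claim, which the documents do not say. If both were required, no split across outcomes would be needed. Whether distinct recommendations, each compared with control, need joint correction is also disputed among statisticians. A reader might infer that a six-test correction is obligatory; the documents do not establish that. What stands is that the claim rule and the coding of the group term are both unstated.

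**Conclusion.** The main point holds. With a two-sided 0.05 test, the inputs in 4.2 require 25-26 evaluable and about 32-33 enrolled per arm against a stated 60. At 60 per arm, power for a standardised difference of 0.8 is about 97-98%, not 80%. The likely explanations are a two-arm total used per arm, an unstated margin or a misreported input; the documents confirm none of them. This is a failure of traceability, not a shortage of participants. No power basis is given for adherence.

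The secondary point holds conditionally. The SAP leaves both primary outcomes at an uncorrected 0.05 by implication, and the group term admits one test or three per outcome. If either outcome suffices for a claim, familywise error is about 7-10% pooled and 17-24% with three contrasts, for an assumed between-outcome correlation of 0.9 down to 0.

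**What to change.** **Protocol 4.2.** State how 60 was reached. Failing that, restate it, marked as a retrospective recalculation:

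*60 per arm (48 evaluable if 20% are lost; 50 if the allowance was n × 1.2) gives about 97-98% power for a between-arm standardised difference of 0.8, or 80% power for about 0.57-0.58 (about 1.4% TEI if the SD is 2.5), for an unadjusted two-sample t-test at two-sided 0.05. The planned analysis is baseline-adjusted with multiple imputation. Adherence was not powered.*

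This is wording only, with no change in enrolment.

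**SAP.** Before group codes are opened, fix the coding of the group term and say whether a claim needs one primary outcome or both. The SAP describes blinding through data handling and imputation and puts the group analyses in the future tense, so this may still be possible; if codes are already open, mark the rule as added afterwards. If either outcome suffices, control error across the week-12 primary tests, for example by Holm, and lift the exemption for pre-specified tests there. That is two tests if pooled and six with three contrasts, where correcting across arms is a matter of judgement. Weeks 1, 2, 4 and 8 stay outside, since the SAP lists them as secondary.

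The cost is stricter thresholds. At the strictest six-test step (0.05/6) with 48 per arm, power for 2% TEI is about 89% at SD 2.5 and 71% at SD 3.0, against 97% and 90% at 0.05. Later Holm steps are less strict.
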